**Table 7.a Visit Windows for Immunogenicity and Safety Analyses by Visit**

Visit	Scheduled Trial Day	Visit Window (Trial Day)		
		Vital Signs b	Immunogenicity	CCI
Baseline a	≤ 1	≤ 1	≤ 1	CCI
Day 28 (Month 1)	28	2-59	2-59	
Day 91 (Month 3)	91	60-135	60-135	CCI
Day 180 (Month 6)	180	136-272	136-272	CCI
Day 365 (Month 12)	365	273-379	273-379	CCI
Day 393 (Month 13)	393	380-466	380-466	
Day 540 (Month 18)	540	≥ 467	467-635	CCI
Day 730 (Month 24)	730		636-912	
Day 1095 (Month 36)	1095		913-1277	
Day 1460 (Month 48)	1460		≥ 1278	

(a) Where time is available, the time of the collection must be prior to the first vaccination of trial drug. Day 1 observations taken after the first vaccination are considered post-baseline values

(b) Vital signs include: systolic blood pressure, diastolic blood pressure, heart rate, body temperature, height and weight.

## 7.2 Analysis Sets

**Randomized Set:** The Randomized Set will consist of all randomized subjects, regardless of whether IP was received (any vaccine administered).

**Safety Set (SS):** The SS will consist of all randomized subjects who received at least one dose of the trial vaccine (including control vaccine). For analyses of solicited AEs and unsolicited non-serious AEs, only subjects in the immunogenicity subset will be included (600 subjects in total [groups 1 and 4: 100 subjects each; groups 2 and 3: 200 subjects each]). SAEs, virologically confirmed dengue and AEs leading to trial or vaccine withdrawal will be assessed for all subjects in the SS. Subjects will be summarized according to the vaccine received.

**Full Analysis Set (FAS):** The FAS will consist of all randomized subjects who received the trial vaccine (including control vaccine) and for whom valid pre-dosing and at least one valid post-dosing blood sample have been received. Subjects will be analyzed according to the group to which they were assigned.

**Per-Protocol Set (PPS):** The PPS will consist of all subjects in the FAS who have no major protocol violations as presented in [Table 7.b](#). The major protocol violation criteria will be defined as part of the blinded data review prior to the unblinding of individual subject's treatment assignment. The categories of major protocol violations include: (1) not meeting selected entry criteria, (2) receiving wrong trial treatment (3) receiving prohibited therapies, and (4) other major protocol violations that may be identified during blinded data reviews.

Both the FAS and PPS will include only subjects from the immunogenicity subset (600 subjects in total [groups 1 and 4: 100 subjects each; groups 2 and 3: 200 subjects each]), i.e., subjects for whom blood samples for assessment of dengue neutralizing antibodies are collected.

The primary analysis of immunogenicity will be based on the PPS, and other supportive analysis will be provided for the FAS.

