## 4.4 Trial Design

This is a Phase II, double-blind, controlled, randomized trial that will enroll 1,800 healthy children aged 2≥ to <18 years old into 1 of the following 4 groups:

- **Group 1 (TDV 2-dose):** receiving a two-dose primary vaccination at Day 1 (M0:Month 0) and Day 91 (M3:Month 3) with the trial vaccine. These subjects will also receive a placebo injection at Day 365 (M12:Month 12).
- **Group 2 (TDV 1-dose):** receiving a one-dose primary vaccination at Day 1 (M0) with the trial vaccine. These subjects will also receive a placebo injection at Day 91 (M3) and Day 365 (M12).
- **Group 3 (TDV 1-dose with booster):** receiving a one-dose primary vaccination at Day 1 (M0) and booster vaccination at Day 365 (M12) with the trial vaccine. These subjects will also receive a placebo injection at Day 91 (M3).
- **Group 4 (Placebo Control):** receiving injections of placebo at Day 1 (M0), Day 91 (M3), and at Day 365 (M12).

Subjects will be randomized to these 4 groups in a 1:2:5:1 ratio as shown in [Table 4.a](#).

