**Table 4.a Number of Subjects per Group**

Group	No. of Subjects	No. of Subjects in the Immunogenicity Subset
Group 1	200	100
Group 2	400	200
Group 3	1,000	200
Group 4	200	100
Total	1,800	600

Randomization will be stratified by age group based on the age at the time of informed consent:

1. 2 to 5 years of age, inclusive,
2. 6 to 11 years of age, inclusive, and
3.  $12 \geq$  to  $<18$  years of age

CCI

Safety evaluation will include documentation of Serious Adverse Events (SAEs) and identification of febrile episodes of potential dengue etiology in all subjects for the trial duration. In addition, all subjects in the immunogenicity subset will be provided with a diary card and will be instructed to record:

- Solicited local adverse events (AEs) for 7 days following vaccination (day of vaccination + 6 days). These will include:
  - infant/toddler/child  $< 6$  years: injection site pain, injection site erythema and injection site swelling.
  - adult and child ( $\geq 6$  years): injection site pain, injection site erythema and injection site swelling.
- Solicited systemic AEs for 14 days following vaccination (day of vaccination + 13 days). These will include:
  - infant/toddler/child  $< 6$  years: fever, irritability/fussiness, drowsiness and loss of appetite.
  - adult and child ( $\geq 6$  years): asthenia, fever, headache, malaise, myalgia.
- Unsolicited AEs for 28 days following vaccination (day of vaccination + 27 days).

Any subject with febrile illness (defined as temperature  $\geq 38^\circ\text{C}$  on 2 consecutive days) will be asked to return to the site for dengue fever evaluation. A dengue infection will be considered virologically confirmed by either positive polymerase chain reaction (PCR) or NS1 enzyme-linked immunosorbent assay (ELISA). A blood sample will be collected within  $\leq 5$  days after the

[figure not shown]
onset of fever to perform virological confirmation of dengue and for hematology and for biochemistry to assess the severity of infection.

Blood samples for the measurement of neutralizing antibodies (immunogenicity) will be collected from a randomly selected subset of 600 subjects (100 subjects in group 1 and group 4 and 200 subjects in group 2 and group 3). CCI [REDACTED]

[REDACTED] Samples for immunogenicity will be taken prior to vaccination and at intervals of 1, 3, 6, 12, 13, 18, 24, 36, and 48 months following the first vaccination. CCI [REDACTED]

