**Duration of Trial:**

For each subject, the duration of the trial will be 48 months and will include a total of 10 protocol-scheduled visits for subjects included in the immunogenicity subset and a total of 7 protocol-scheduled visits for subjects not included in the immunogenicity subset.

Interim analyses on cleaned safety and immunogenicity data CCI [REDACTED] are planned on data up to Month 6, and on data up to Month 18 (see Section [7.13](#)).

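### All-subject safety percentages pool two follow-up modes in different proportions (subset share 20% in Group 3, 50% elsewhere); the effect is probably small, but a by-subset display is needed for contrasts with Group 3

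*SAP*

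**What the plan says.** - **Allocation (4.4).** "Subjects will be randomized to these 4 groups in a 1:2:5:1 ratio", giving 200, 400, 1,000 and 200 subjects.
- **Subset (4.4, Table 4.a).** Neutralizing antibodies are measured in a "randomly selected subset of 600 subjects", made up of "100 subjects in group 1 and group 4 and 200 subjects in group 2 and group 3".
- **Extra follow-up in the subset.** Under 4.4, "all subjects in the immunogenicity subset will be provided with a diary card". The card covers local reactions for 7 days, systemic reactions including fever for 14 days, and unsolicited events for 28 days after each injection. The trial duration paragraph gives "a total of 10 protocol-scheduled visits for subjects included in the immunogenicity subset". For everyone else it plans "a total of 7 protocol-scheduled visits for subjects not included in the immunogenicity subset". Appendix A shows that the three additional visits are at Months 1, 6 and 13.
- **Outcomes on everyone (7.2).** SAEs and confirmed dengue are taken over the whole Safety Set, and the same sentence adds that "AEs leading to trial or vaccine withdrawal will be assessed for all subjects in the SS". Section 7.11 tabulates safety by trial group unless otherwise specified. It specifies no split by subset membership for these outcomes.
- **Common surveillance.** Section 4.4 applies SAE documentation and detection of possible dengue fever to all subjects throughout. Tables A-1 and A-2 use the same fever trigger for blood sampling, and both schedule monthly calls where there is no visit.

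**The concern.** The subset is drawn at random, but the sampling fraction differs by group. The mix of follow-up modes inside an all-subject percentage is therefore fixed by design: one fifth intensive in Group 3, one half in each other group. If events are detected less completely outside the subset, Group 3 shows a lower percentage even when true risk is the same. Groups 1, 2 and 4 share one mix, so contrasts among them are unaffected.

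Group 3 is the booster arm and the largest group, and section 6.0 gives an adequate safety database before Phase III as one purpose of the sample size. An artefact that could make this arm look safer deserves a check.

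Two outcomes are the most exposed:

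- **Dengue with onset before Day 30**, which 7.11.5 reports as its own category. In that period subset members record temperature daily for 14 days and attend a Month 1 visit; the others receive a Month 1 call.
- **Withdrawals due to non-serious adverse events.** Section 7.11.1 counts any event collected in the trial towards withdrawal from the trial, but diary collection of non-serious events exists only in the subset.

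**Working it through.** **1. Table 4.a reproduced.** 1,800 × 1/9, 2/9, 5/9, 1/9 = 200, 400, 1,000, 200, as printed. Subset shares f:

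| Group | Subset / total | f |
|---|---|---|
| 1 | 100/200 | 50% |
| 2 | 200/400 | 50% |
| 3 | 200/1,000 | 20% |
| 4 | 100/200 | 50% |
| All | 600/1,800 | 33.3% |

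**2. Scheduled contacts, Month 0 to Month 48 (Appendix A).**
- Subset (Table A-1, note p): 10 visits. Calls at M2, M4, M5 (3), M7–11 (5), M14–17 (4), M19–23 (5), M25–35 (11), M37–47 (11) = 39. Total 49.
- Outside (Table A-2, note k): 7 visits. Calls at M1, M2 (2), M4–11 (8), M13–17 (5), M19–23 (5), M25–35 (11), M37–47 (11) = 42. Total 49.

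Each schedule has one contact in every month. They differ in mode at 3 of 49 contacts (M1, M6, M13), plus the diary card.

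**3. Effect of the mix.** Let s be detection outside the subset relative to inside. The SAP does not give s, so it is an assumption. With equal true risk, observed/true rate = f + (1 − f)s, and

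Group 3 / other group = (0.2 + 0.8s) / (0.5 + 0.5s).

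| s | Group 3 | Others | Ratio |
|---|---|---|---|
| 1 | 1.00 | 1.00 | 1.00 |
| 0.95 | 0.96 | 0.975 | 0.985 |
| 0.9 | 0.92 | 0.95 | 0.968 |
| 0.8 | 0.84 | 0.90 | 0.933 |
| 0.5 | 0.60 | 0.75 | 0.80 |
| 0 | 0.20 | 0.50 | 0.40 |

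The last two rows only show how the formula behaves; nothing in the SAP points to them. For scale, a true rate of 2% with s = 0.8 gives 1.68% in Group 3 and 1.80% elsewhere.

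**4. Reach of the diary.** Three 28-day windows are 84 days; 84/1,460 = 5.8% of follow-up. Suppose events are spread evenly and the diary doubles detection inside its windows only (both assumptions). Subset detection relative to non-subset is then 1 + 0.058 = 1.058, and the ratio is (0.2 × 1.058 + 0.8)/(0.5 × 1.058 + 0.5) = 1.012/1.029 = 0.98. The position differs for dengue before Day 30: temperature recording covers 14 of Days 1–29, or 48% of that period.

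**5. What stratifying does.** Within the subset, or within the non-subset, every group has one follow-up mode. If s is the same in all groups, the within-stratum ratio under equal true risk is 1.00 for any s.

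**The case against.** The case against acting is substantial.

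- **Equal contact frequency.** The visit counts of 10 and 7 suggest a larger gap than exists. With 49 contacts each, all-subject SAE and fever surveillance, one fever trigger and one PCR/NS1 definition, the design aims at like-for-like capture of SAEs and dengue. This stands, and limits the point for those two outcomes.
- **Withdrawals have another route.** Section 7.3 tabulates the primary reason for discontinuation, with adverse event as a category, for all randomized subjects. Table A-2, note j, includes adverse events in the site review outside the subset. This weakens the withdrawal argument. It does not make collection identical, because a non-serious event is prompted by a diary in one cohort and not in the other.
- **Descriptive trial.** Section 7.1 rules out inferential analysis, so no error rate is affected. This stands, but the by-group percentages are the reported safety result, and readers will set them side by side.
- **Chance is larger.** At a 2% rate Group 4 expects 200 × 0.02 = 4 events, so a ratio of 0.97 is far inside random variation. This also stands, and argues for a modest remedy.
- **Partly handled already.** Dengue is also tabulated by baseline serostatus. The SAP describes baseline titers only for the subset, so those tables in effect hold follow-up mode constant. They do not cover SAEs or withdrawals.

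A reader might infer more: that all three outcomes are materially under-counted in Group 3, with ratios of 0.80 or 0.88. Those figures need subset detection to be 2 or 1.5 times that outside, and the SAP gives no basis for either value.

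**Conclusion.** The point holds in a limited form. The unequal shares are exact, follow-up differs by subset membership, and no by-subset summary of the pooled outcomes is planned. Crude contrasts with Group 3 can therefore be affected by follow-up mode; if detection is lower outside the subset, the direction favours Group 3.

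For SAEs and overall dengue the effect is likely small: a Group 3 ratio of 0.97 to 1.00 when s is 0.9 to 1. That range for s is a judgement based on the matched contact schedule, not a figure in the SAP. For dengue before Day 30 and withdrawals due to non-serious events a gap is more plausible, but its size cannot be found from the document. The calculations assume equal true risk and the same s in every group.

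**What to change.** In SAP 7.2 and 7.11:

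1. Keep the crude all-subject n/N by group.
2. Add the same summaries by group within subset and within non-subset, at least for adverse events leading to withdrawal, SAEs within 28 days of a vaccination, and virologically confirmed dengue with onset before Day 30.
3. State that comparisons with Group 3 on these outcomes rest on the within-stratum figures.

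No reweighted overall column is needed. Standardising rare-event percentages would add complexity to descriptive tables for little gain once the strata are shown.

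The cost is SAP wording and one classification variable that the trial already holds. The downside is sparser cells: 100, 200, 200 and 100 subjects in the subset and 100, 200, 800 and 100 outside it, so Groups 1 and 4 have only 100 per stratum.

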### **7.2.1 Major Protocol Violations**

A major protocol violation is considered to have a significant impact on the immunogenicity results of the subject. All protocol deviations will be identified prior to unblinding and a clinical judgment will be necessary to classify each deviation as "major" or not. These deviations and the judgment regarding their use will be listed and summarized in the final clinical trial report.

The criteria described in this section will be used to identify subjects with major protocol violations which could impact the analysis of the primary endpoint. Subjects meeting these criteria will be excluded from the PPS described above. Subjects meeting these criteria will be identified and approved prior to database lock and unblinding.

**Table 7.b Criteria for Exclusion from the PPS**

Criteria for exclusion	Probable Method of identification
Missing Dengue-neutralizing titers for all 4 serotypes at baseline.	Identified programmatically using immunogenicity data
Missing Dengue-neutralizing titers for all 4 serotypes at Months 1, 3, 6, 12, 13 and 18.	Identified programmatically using immunogenicity data.
Month one immunogenicity sample is NOT collected within $\pm$ 5 days of the scheduled Month 1 (Day 30) visit.	Identified programmatically using immunogenicity data.
Not receiving all investigational vaccine administrations [Day 1 (M0), Day 91 (M3) and Day 365 (M12)].	Identified programmatically using dosing data.
Not receiving the assigned treatment/dosing schedule [refers to correct administration of active or placebo into the correct arm on Day 1 (M0), Day 91 (M3) or Day 365 (M12)].	Identified programmatically using blinded IVRS data and/or through source documents provided in blinded fashion to the statistician
Not receiving the correct dosage of the investigational vaccine. This refers to improperly prepared syringes at the site pharmacy.	Identified through source documents and provided in blinded fashion to the statistician.
Subject meets any of exclusion criteria 2d, 3, 4 or 5 (subject to blinded medical review).	Subjects identified programmatically using CRF-recorded data. Subjects will be identified before unblinding, and a blinded review list sent for clinical science review to determine evaluability status for each identified subject. Note that exclusion criteria 2d and 3 identify subjects' use of prohibited medications prior to enrollment.
Use of prohibited medications during the trial (subject to blinded medical review).	Potential prohibited medications ( Appendix C ) to be identified by sending a blinded review list of CRF-recorded concomitant medication data for clinical science review to determine evaluability status for each identified subject.

Other major violations may be identified based on blind data reviews of deviation log subject to medical review.

### **7.3 Disposition of Subjects**

Disposition of all screened subjects will be summarized descriptively, which includes a summary of the number of screened subjects, the number of randomized subjects, the number of subjects completing all planned vaccine regimen and the number of subjects completing all planned trial visits. Disposition of non-randomized subjects will be summarized according to screen failure reason, including primary reason for screen failure [adverse event, screen failure (did not meet inclusion/did meet exclusion criteria), withdrawal by subject, trial terminated by sponsor, and other].

Disposition of all randomized subjects will be summarized by the 4 groups overall and within each age stratum. The categories will include:

- Number of randomized subjects
- Number of subjects completing the trial vaccine
- Number of subjects who prematurely discontinue trial vaccine
- Primary reason for premature discontinuation of trial vaccine
- Number of subjects completing all planned trial visits
- Number of subjects prematurely discontinue all planned trial visits
- Primary reason for premature discontinuation of all planned trial visits

A subject is to be assumed ongoing unless he/she completed the end of trial CRF, indicating either completion or early terminated. The Primary reasons for discontinuation of trial medication/visits will be summarized, and the categories include adverse event, lost to follow-up, protocol violation, trial terminated by sponsor, withdrawal by subject, and other. Number of screened/enrolled, randomized and analysis populations will also be presented.

#### 7.4 Demographic and Baseline Characteristics

Demographic and baseline characteristics will include age, sex, race, weight, height and BMI, which is calculated based on both weight and height measurements from baseline, and will be summarized descriptively by group overall and within each age stratum based on the randomized set and PPS.

In addition, the same tables will be produced based on the baseline seropositive status (seropositive or seronegative). A sample is considered seropositive, if  $MNT_{50} \geq 10$ . A subject who is positive for at least one of four DENV serotypes is categorized as a seropositive subject.

Summary statistics (number of subjects [N], mean, median, SD, minimum, and maximum) will be generated for continuous variables (age, height, weight, BMI and other), and the number and percentage of subjects within each category will be presented for categorical variables (sex, race and other).

Individual demographic data will be presented in the data listing.

Demographic and baseline characteristics of screen failure subjects and reasons for screen failures will be summarized total overall for subjects who are screened, but not enrolled in the trial. Individual demographic data, date of informed consent, any available safety data and reason for screen failure will also be presented in the data listing.

#### 7.5 Medical History and Concurrent Medical Conditions

Medical history and concurrent medical conditions will be coded using the Medical Dictionary for Drug Regulatory Activities (MedDRA, Version 16.1, or higher) coding system.

All medical history and concurrent medical condition data will be listed by trial site, and subject number. The listing will contain subject identifier, treatment arm, system organ class (SOC),

whether there was any significant medical history or concurrent condition, and if yes, a detail of the medical history or concurrent condition.

## 7.6 Medication History and Concomitant Medications

Medication history and concomitant medications will be coded using the World Health Organization DRUG dictionary (WHO Drug Version March 2013, or higher).

Separate listings for medication history and concomitant medications will be produced by trial center and subject number. The listings will contain subject identifier, treatment, WHO Drug preferred term (PT), dose, frequency, unit, route, stop date, and reason for use.

## 7.7 Investigational Product Exposure and Compliance

The investigator records all injections of investigational vaccine given to the subject in the eCRF. Compliance rate will be summarized by the 4 trial vaccination groups, by presenting the number and percentage of subjects receiving all three doses of vaccination and the number and percentage of those receiving only the first and first two doses of vaccination. The vaccination date/time information will be listed for each subject. The duration of follow-up will be summarized as a continuous variable, and also in the following categories: (1) 1 – 180 days, (2) 181 – 365 days, (3) 366 - 540 days, (4) 541 - 730 days, (5) 731 - 1095 days, and (5) > 1096 days. The follow-up is defined as the number of days since the first vaccination to the end of trial visit. For interim analysis, if the end of trial visit dates are not reported, the date of data cutoff will be used for calculation.

## 7.8 Efficacy Analysis

Not applicable

## 7.9 Pharmacokinetic/Pharmacodynamic Analysis

Not applicable

## 7.10 Other Outcomes

### 7.10.1 Immunogenicity

The primary immunogenicity endpoint in the trial is GMTs of neutralizing antibodies (MNT50) for each of the four DENV serotypes. The secondary endpoint is seropositivity rates (%) for each of the four DENV serotypes where seropositivity is defined as a reciprocal neutralizing titer  $\geq 10$ . A value of 5 (midpoint between 0 and the lower limit of detection) will be used for Dengue Neutralizing Antibody titers which are below the lower limit of detection (10).

Subjects included in the immunogenicity subset (100 subjects in group 1 and group 4 and 200 subjects in group 2 and group 3) will undergo blood sampling for serological immunogenicity testing at Months 0, 1, 3, 6, 12, 13, 18, 24, 36, and 48.

[figure not shown]
For the immunogenicity subset of subjects, descriptive statistics and 95% CIs for GMTs and seropositivity rates will be computed by treatment group at Months 0, 1, 3, 6, 12, 13, 18, 24, 36, and 48. The 95% CI of seropositivity rate will be calculated based on Clopper-Pearson method. GMTs will be calculated, for each relevant time point as anti-logarithm of  $\sum(\log \text{transformed titer}/n)$ , where n is the number of subjects with titer information. The 95% CI for GMTs will be calculated as the anti-log transformation of upper and lower limits for a two-sided CI of the mean of the log-transformed titers. In addition, the percent of subjects with monovalent (seropositive for only one of the four DENV serotypes), bivalent (seropositive for any two of the four DENV serotypes), trivalent (seropositive for any three of the four DENV serotypes), and tetravalent (seropositive for all four DENV serotypes) seropositivity, as well as at least bivalent (seropositive for  $\geq 2$  DENV serotypes) and at least trivalent (seropositive for  $\geq 3$  DENV serotypes) seropositivity will be summarized by treatment group at each visit. Additional summaries of immunogenicity endpoints by baseline seropositive status (seropositive or seronegative) will also be provided.

The primary immunogenicity analysis will be performed on the PPS. A supportive analysis will be provided using the FAS.

GMTs will also be presented graphically for each serotype overall and by baseline seropositive status. In addition, reverse cumulative distribution curves will be plotted separately for each trial group and serotype by baseline seropositive status for all the time points except the baseline.

